# 5.1.5.2.3 Other Quality of Life Related Secondary Measures

a) Health Utilities Index (HUI). The Health Utilities Index, Mark 3 (HUI3) is a 21-item generic health instrument for determining overall utility associated with particular health states [Furlong, 2001]. The HUI questionnaire is composed of eight attributes of high importance to members of the general population: vision, hearing, speech, ambulation, dexterity, emotion, cognition, and pain. A preference-based scoring function, based on multi-attribute utility theory, allows one to converts questionnaire responses into a measure of overall health utility, which can then be used to calculate quality-adjusted life years (QALYs) in clinical trials.

The Health Utilities Index (HUI) has been validated and used in many observational studies and clinical trials sponsored by NIH. A number of ongoing CKD and ESRD studies are using the HUI, including Intensive vs. Conventional Renal Support in Acute Renal Failure: Economic Analysis, Assessing QALY in Chinese renal failure patients (Hong Kong), Pilot Study of Chronic Renal Insufficiency and Functional Abilities in Renal Subjects (F.A.I.R.S.). Cost effectiveness is commonly used to determine the potential advantage of a new technology compared to standard therapies. The Health Utilities Index will be obtained at baseline, and months 4 and 12.

- b) Feeling Thermometer. The feeling thermometer is a single question that asks patients to rate their own health on a visual analog scale from 0 to 100 with 0 being dead and 100 being perfect health [Baldassarre, 2002;Schunemann, 2003]. The feeling thermometer has been used in numerous studies to permit patients to provide preference ratings of their own health status (health utilities). Although it has not been shown to discriminate between dialysis modalities [Churchill 98], it has demonstrated responsiveness to therapy in multiple health states[Baldassarre, 2002;Schunemann, 2003]. Thus, the change from baseline to month 12 in feeling thermometer score will be used as an additional secondary outcome in this trial. The feeling thermometer will be obtained at baseline, months 4 and 12.
- c) Sleep. The Medical Outcomes Study (MOS) Sleep Scale is an 12-item measure that includes items on sleep initiation and maintenance, sleep adequacy, daytime somnolence, and respiratory disturbance; 10 items of the instrument are summed to obtain an overall sleep score (Sleep Problems Index) [Unruh, 2003]. Subjects are instructed to relate responses to sleep habits over the previous month. The SPI showed good internal consistency reliability (Cronbach's alpha = 0.70) and discriminative validity, with lower (worse) overall sleep scores in HD patients versus patients without known kidney disease [Unruh, 2003]. Self-reported sleep complaints have been noted to have similar frequency between different dialysis modalities [De Vecchi, 2000]. The MOS Sleep Scale will be performed at baseline, months 4 and 12.

### 5.1.5.3 Nutritional Status

There is no ideal nutritional marker, due to the lack of a single variable that is easily performed, reproducible, inexpensive and can predict outcomes. Thus, most studies rely on a combination of nutritional markers to assess nutritional status. Some of the markers that have been used include the Subjective Global Assessment (SGA), normalized protein catabolic rate (nPCR), measures of body size, including height, weight and body mass index (BMI) and measures of lean body mass such as duel energy x-ray absorptiometry (DEXA), multifrequency bioimpedance (BIA), anthropometrics and creatinine kinetics and. In addition, nutritional status is affected by the presence of inflammation and a variety of markers have been used to measure inflammation. C-reactive protein (CRP) is the most commonly measured inflammatory marker in dialysis patients.

The normalized protein catabolic rate has been used in dialysis patients for many years as a measure of dietary protein intake. It is much easier to determine dietary protein intake from nPCR than from diet records, interviews by dietitians or by using food frequency questionnaires. [Panzetta, 1990] The use of the nPCR assumes, however, that the patient is in neutral nitrogen balance, an assumption that is not always met and an assumption that has not been tested in nocturnal hemodialysis patients. In addition, there is now evidence that a low nPCR is not associated with an increased risk of mortality in chronic hemodialysis patients. [Pifer, 2002;Rocco, 2004] Therefore, in this study, nPCR will be used as a surrogate for dietary protein intake. The change in nPCR over 12 months will be determined. The same method used in the HEMO Study will be used to determine nPCR values. nPCR will be calculated on a monthly basis.

Higher BMI has been shown to be protective in chronic dialysis patients, a finding that is contrary to that found in the general population. [Cheung, 2000; Hakim, 1999;Kopple, 1997;Sarnak, 2000] In the HEMO Study, the mean post-dialysis weight declined by about 2.7 kg at three years under the informative censoring model, with no significant differences between the randomized treatment groups through year 3. [Rocco, 2004] In addition, there was an association between an increased risk of mortality and a lower cross-sectional BMI level in the range below 25 kg/cm^2. Also, declining BMI was associated with an increased risk of mortality, on average, regardless of either the patient's current or 12 month prior BMI level. The measurement of BMI is confounded in dialysis patients, however, by the presence of both muscle wasting and excess fluid weight. In CKD patients with residual renal function that allowed for the collection of 24 hour urine for creatinine excretion, the survival advantage for patients with high BMI was found only in those patients with low body fat and in the low BMI group, high body fat and low muscle mass were associated with an increased risk of death. [Beddhu, 2003] These data imply that maintenance or increasing muscle mass and/or lowering body fat may be important in decreasing mortality rates in dialysis patients and that measurement of lean body mass will be an important outcome to measure in this study (see below). BMI will be calculated on a monthly basis.

Of the several measures that can be used to assess lean body mass, DEXA is the most reliable. [Kerr, 1996] DEXA is not routinely available, [Jones, 2002] however, and no studies have been performed to determine if lean body mass, as measured by DEXA, is predictive of outcome in dialysis patients. Single frequency bioimpedance has been shown to be associated with both morbidity and mortality in dialysis patients. [Chertow, 1997;Ikizler, 1999] However, all bioelectrical impedance methods employ some form of predictive modeling to obtain estimated outcomes. Thus, large errors in individual limit its clinical use, especially when persons are monitored repeatedly. The predictive errors for an individual are large so that repeated estimates are insensitive to small responses to treatment. [Chumlea 2004, in press] In addition, BIA may not be very precise for measuring body composition in both underweight and obese patients since height and weight are major sources of variation in the BIA prediction models [Guida, 2001].

Anthropometrics were used to measure body composition in the HEMO Study. In this study, the mean levels of both upper arm and calf circumference declined throughout three years of follow-up in all treatment groups, although the decline was less in the high flux group for upper arm and calf circumferences (by  $0.35 \pm 0.16$  cm (p = 0.031) and  $0.31 \pm 0.13$  (p = 0.015) respectively, representing 1.2% and 0.9%, respectively of the mean baseline values for these factors). [Rocco, 2004] Anthropometrics can also be used to obtain information on subcutaneous fat thickness on the limbs and trunk (triceps and subscapular skinfolds), internal adipose tissue (abdominal circumference), [Després, 1991] midarm muscle area (combination of midarm circumference and triceps skinfolds), frame size (elbow breadth) [Chumlea, 2002] and knee height (to estimate stature in amputees or patients unable to stand) [Chumlea, 1994;Chumlea, 1998]. Calf circumference is an indirect measure of muscle mass [Patrick, 1982] and fat free muscle mass can be calculated when the measurements for biceps, triceps, subscapular and suprailiac skinfolds are obtained [Heymsfield, 1982]. These latter calculations are also susceptible to the same criticisms noted above for bioimpedance for specific patient subgroups such as obese and underweight patients. In addition, anthropometry is more time-consuming than bioimpedance and the calculation of fat free mass cannot be done if one of the four skinfold measures is unable to be obtained. This situation occurred in about 10% of the HEMO Study patients [Rocco, 2004]. For this study, single frequency BIA should be performed at baseline, 4 months and 12 months. The BIA is not required for

randomization. All measurements should be carried out immediately prior to a mid week dialysis treatment (Wednesday or Thursday) in the recumbent position for patients in the standard arm of the study.

## 5.1.5.4 Mineral Metabolism

Three other aspects of mineral metabolism will be measured in this study: Changes in the use of phosphate binders, change in serum calcium level and change in serum PTH level. As noted in 5.1.3.4 above, the serum phosphorus level can be influenced by the use of phosphate binders. The type and amount of phosphate binders will be collected at baseline, months 4 and 12 in all patients. This information will be important since the rate of progression of coronary artery and aortic calcification was greater in patients receiving large oral doses of calcium-containing compounds versus sevelamer. [Chertow, 2002; Chertow, 2003] It is anticipated that there will be a decrease in the number of phosphate binders prescribed in patients in the nocturnal arm of the study. [Mucsi, 1998] Although there is also likely to be an increase in protein and thus phosphorus intake in nocturnal study patients, financial constraints do not allow for the determination of phosphorus intake over time in this patient cohort.

Hypercalcemia is a risk factor for mortality in chronic hemodialysis patients [Block, 2004;Foley, 1996]. The use of calcium-based phosphate binders increases the risk of hypercalcemia, [Chertow, 2002;Chertow, 2003] and hypercalcemia is also a risk factor for vascular calcification. [Raggi, 2002] Conversely, most studies have not shown a relationship between hypocalcemia and mortality. Nocturnal dialysis patients are at risk for hypocalcemia, and a higher dialysate calcium level is needed to help prevent this problem. [Al Hejaili, 2003] Thus, serum calcium levels will be obtained on a monthly basis. If there is more than one value in a particular month, then the first value of the month will be used for analytic purposes. The percentage of patients with normal serum calcium levels with normal serum calcium levels during months 1 and 2 and compared to the percentage of patients with normal serum calcium levels during months 4 – 6 and months 10 - 12.

There is evidence that both hyperparathyroidism and hypoparathyroidism is associated with an increased risk of death. Dialysis patients with hyperparathyroidism are more likely to develop myocardial fibrosis [Amann, 1994] and patients with an elevated PTH level have an increased risk for all cause and cardiovascular mortality. [Block, 2004; Ganesh, 2001] More recent studies have also shown an association of hypoparathyroidism (defined differently by each investigator) and cardiac morbidity and mortality. [Guh, 2002; Tsuchihashi, 2000] One hypothesis for this observation is that hypothyroidism leads to adynamic bone disease that prevents the uptake of serum calcium. This loss of bone buffering results in the availability of calcium for deposition into blood vessels and soft tissues. Thus, the percentage of patients with normal serum PTH levels will be determined at baseline and months 1 and 2 and compared to the percentage of patients with normal PTH levels during months 4 - 6 and months 10 - 12. In addition, the use of vitamin D analogues will be ascertained during these same time intervals.

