## d) Dialysate Composition

In the conventional home hemodialysis group, standard dialysis baths will be used per local protocol and based on the patient's monthly laboratory values. In the nocturnal home hemodialysis group, there will be a more frequent monitoring of electrolytes (potassium, calcium, phosphorus) during training and the first two months of nocturnal therapy. Nocturnal hemodialysis is known to decrease serum phosphate and even lead to hypophosphatemia. Persistently low serum phosphate may lead to weakness, osteomalacia and in extreme cases hemolysis. In addition, nocturnal hemodialysis can lead to negative calcium balance due to calcium loss through ultrafiltration. This may lead to increase in PTH and alkaline phosphatase levels, as well as a decline in bone density as measured by DEXA. Conversely, overzealous supplementation of calcium through the dialysate can lead to low bone turnover. Anecdotal experience suggests that the desirable intact PTH levels for nocturnal hemodialysis should be at the lower range or below the KDOQI (2006 dialysis update) guidelines currently at 150-300 pg/mL or 16.5-33 pmol/L. Therefore, a standard protocol will be used for monitoring the levels of phosphorus, calcium and PTH and for the adjustment of dialysate calcium and phosphorus levels.

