## Patient follow-up

The dialysate calcium level will be adjusted until the PTH level is in the target range. A modestly elevated post dialysis serum calcium level is acceptable to achieve this goal.

In the absence of pre-dialysis hypercalcemia, strive for a lower PTH target by increasing dialysate calcium if either the alkaline phosphatase of bone origin is still elevated and/or bone density by DEXA is significantly lower than in the previous study.

The dialysate phosphate level will be adjusted until both the pre- and post-hemodialysis phosphate levels are within normal limits.

In the absence of pre-dialysis hypercalcemia, and in the presence of high PTH and alkaline phosphatase levels, use a higher dialysate calcium is recommended before resorting to high dose vitamin D analogues. Otherwise use Vitamin D analogues in accordance with NKF K/DOQI guidelines.

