a) Vascular Access Complications: Access infection, stenosis, thrombosis, and intervention will be defined, and a detailed protocol developed to monitor and treat these complications in both groups. The primary measure of vascular access complications will be primary unassisted patency rate (time to first access intervention). Groups will also be compared with respect to: number of access interventions per patient years, time to first thrombosis related access failure, and number of thrombosis related access failures per patient years,

number of access infections per patient years, number of infection related access failures per patient years, time to first infection related access failure.

- b) Iron Losses: Patients on daily hemodialysis have been shown to have increased iron losses compared with conventional patients. Iron utilization will be documented in both groups.
- c) Malnutrition: Although it is anticipated that nutritional status will improve with nocturnal hemodialysis, the potential for malnutrition exists. There may be increased dialytic losses of amino acids due to increased clearances provided with nocturnal hemodialysis. Thus, nutritional status, as outlined in Sections 5.1.3.3 and 5.1.5.3, will be monitored on a regular basis.
- d) Patient Burn-Out: Patient fatigue is a potential concern with the increased frequency of treatments with nocturnal hemodialysis, especially with the requirement that the patients perform the dialysis treatments themselves. The proportion of patients who require a change in dialysis modality lasting more than 2 weeks (back to conventional hemodialysis or to peritoneal dialysis) will be assessed along with reasons for modality change.
- e) Calcium and phosphorus balance: Nocturnal hemodialysis is known to decrease serum phosphate and even lead to hypophosphatemia. Persistently low serum phosphate may lead to weakness, osteomalacia and severe hypophosphatemia (defined as a serum level < 1.0 mg/dl) may cause hemolysis, acute respiratory failure, myocardial depression, or seizures. In addition, nocturnal hemodialysis can lead to negative calcium balance due to calcium loss through ultrafiltration. This may lead to increase of PTH and alkaline phosphatase. These laboratory parameters will be monitored on a regular basis as outlined in Section 3.4.1.d.

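### Section 5.1.5.4 links both high and low PTH to death, but its only categorical summary is a percentage normal, with no stated range, that pools the two tails

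*Protocol*

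**What the plan says.** Protocol section 5.1.5.4 gives the reason for following PTH: "There is evidence that both hyperparathyroidism and hypoparathyroidism is associated with an increased risk of death". Its categorical summary is that "the percentage of patients with normal serum PTH levels will be determined at baseline and months 1 and 2", to be compared with the percentage in months 4-6 and months 10-12. The section does not define normal and does not ask for separate percentages above and below range.

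The same section also lists, among the further aspects of mineral metabolism to be measured, "change in serum calcium level and change in serum PTH level". Table 8 lists parathyroid hormone itself under mineral metabolism. Section 9.5 analyses quantitative outcomes as change from baseline to 12 months.

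Elsewhere the protocol expects that PTH may move either way on nocturnal dialysis:

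- **Upwards.** Section 3.4.1 d, on negative calcium balance: "This may lead to increase in PTH and alkaline phosphatase levels". Section 5.3 e repeats it: "This may lead to increase of PTH and alkaline phosphatase".
- **Downwards.** Section 3.4.1 d warns that "overzealous supplementation of calcium through the dialysate can lead to low bone turnover". On anecdotal experience, it adds that "desirable intact PTH levels for nocturnal hemodialysis should be at the lower range or below the KDOQI" range, given as 150-300 pg/mL.
- **Titration.** The patient follow-up text in 3.4.1 d adjusts dialysate calcium until PTH reaches its target range. It goes lower only on conditions, namely a bone-derived alkaline phosphatase that stays high and/or a significant fall in DEXA bone density: "In the absence of pre-dialysis hypercalcemia, strive for a lower PTH target by increasing dialysate calcium if either the alkaline phosphatase".

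**The concern.** The stated reason for watching PTH has two sides, and the categorical summary has one. A patient who leaves the range downwards and one who leaves it upwards are counted alike, and patients who cross from one tail to the other drop out of the comparison altogether.

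This matters more here than for a typical laboratory value, because the nocturnal arm is managed towards lower PTH. If normal is read as 150-300 pg/mL, the only PTH range in the document, then a nocturnal patient at a level that 3.4.1 d calls desirable, below 150, is scored as not normal. The percentage would then count against the arm for reaching its own goal. In a different mix of patients it could look better while the low tail grows.

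At stake is how the PTH description is read, in particular how many patients end up on the low side, where section 3.4.1 d warns of low bone turnover. No confirmatory result is involved.

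**Working it through.** The protocol gives no PTH mean, SD, category percentages or power figure, so there is no planned figure to reproduce. The check is on what the percentage normal can and cannot show.

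**Inputs**
- From the protocol: range 150-300 pg/mL (3.4.1 d); 90 patients allocated 1:1 (2.2, 2.4.1), so 90/2 = 45 per arm.
- Assumed, not in the protocol: that normal means 150-300 pg/mL; log-normal PTH with log-SD 0.6, 0.8 or 1.0; all medians below; the 40% in step 2.

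**Step 1: identity.** Below + within + above = 100%, so change(within) = -[change(below) + change(above)]. The change in percentage normal fixes only the sum of the two tail changes.

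**Step 2: bound with no distribution.** If the median lies in range, below ≤ 50% and above ≤ 50%. If within = 40%, then below + above = 60%, so below lies between 60 - 50 = 10% and 50%. In 45 patients that is 4.5 to 22.5.

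**Step 3: log-normal illustration.** With median m and log-SD s:

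- below = Φ[(ln 150 - ln m)/s]
- above = 1 - Φ[(ln 300 - ln m)/s]
- within = 100% - below - above

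Worked case, s = 0.6. At m = 400, below/within/above = 5.1/26.5/68.4%. At m = 200 they are 31.6/43.5/25.0%. The changes are +26.5, +17.0 and -43.5 points.

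Changes in percentage points for log-SD 0.6 / 0.8 / 1.0:

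| Median, pg/mL | Within | Below | Above |
|---|---|---|---|
| 400 to 200 | +17.0 / +8.5 / +4.7 | +26.5 / +24.9 / +22.3 | -43.5 / -33.4 / -27.1 |
| 250 to 180 | 0 / 0 / 0 | +18.3 / +14.8 / +12.3 | -18.3 / -14.8 / -12.3 |
| 250 to 120 | -13.0 / -6.4 / -3.6 | +44.8 / +34.8 / +28.4 | -31.7 / -28.4 / -24.8 |
| 250 to 350 | -10.2 / -5.0 / -2.7 | -11.8 / -11.7 / -10.6 | +22.1 / +16.7 / +13.4 |

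**Reading the table.** In the first row the percentage normal improves while the low tail grows by 22 to 27 points. The second row is complete cancellation: 250 × 180 = 45,000 = 150 × 300, so the two medians mirror each other about √45,000 ≈ 212 pg/mL. The last two rows give falls of similar size in the percentage normal from opposite movements.

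**Step 4: what the change in PTH level adds.** It would tell rows three and four apart. In row one it would show a fall from a high level, which agrees with the improved percentage normal. Neither summary then gives the share below 150.

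**Step 5: data.** Table 9 C schedules PTH at baseline and months 2, 5, 8 and 11. Month 2 serves months 1-2, month 5 serves months 4-6, and month 11 serves months 10-12.

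**The case against.** The best case against the point is that the percentage normal is not the plan's only view of PTH. Section 5.1.5.4 names the change in level, Table 8 lists PTH itself, and section 9.5 analyses the change to 12 months. Section 9.1 promises box plots, density estimates and histograms for quantitative variables, and frequency tables and ordered-category models for categorical ones. A large one-way shift would be plain in the level. For a fully cancelled shift from a geometric mean of 350 to 129 pg/mL, a comparison of mean log PTH with 36 per arm (80% of 45) has power of about 0.99 or more over log-SD 0.6 to 1.0. Where risk is two-sided, the share in neither extreme is also a sensible summary, and the section uses the same format for calcium. A breakdown by tail could be added in an analysis plan that is not shown.

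Much of this stands. A reader might infer that the protocol is blind to the low tail, and the documents do not support that: the level is analysed, and the general displays could show part of the distribution. A reader might also infer that low PTH could go unmanaged. That is not supported either, because 3.4.1 d adjusts dialysate calcium to each patient's results and 5.3 e calls for regular laboratory monitoring.

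What does not stand is that this is only missing detail. The protocol fixes a specific summary straight after citing risk on both sides, and that summary can point the wrong way. The change in level does not give the proportion below range, and section 9.1 is general and does not name PTH. For a smaller cancelled shift (259 to 174 pg/mL), power on mean log PTH is only 0.40 to 0.81 with 36 per arm.

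**Conclusion.** The point holds as a minor one. The only categorical PTH summary pools two tails that the section itself treats as separate risks, its range is undefined, and a nocturnal patient at the level the protocol calls desirable may be scored as not normal. In the illustration, the percentage normal can rise by 5 to 17 points, or not move at all, while the share below 150 pg/mL rises by 22 to 27 or 12 to 18 points respectively.

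These sizes rest on assumed medians, an assumed log-normal shape and log-SD, and on reading normal as 150-300 pg/mL. The identity in step 1 rests on none of these. Complete cancellation needs medians that mirror each other about 212 pg/mL. In the other cases shown the percentage does move, but does not say which tail is responsible, so it would be wrong to infer that masking is usually total.

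Nor does this touch the trial's conclusions. Serum phosphorus is the main outcome of the mineral metabolism domain, and section 9.4 treats other outcomes within a domain as exploratory. No primary or main secondary result changes.

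**What to change.** In section 5.1.5.4, replace the percentage of patients with normal PTH by the percentages below, within and above 150-300 pg/mL, the KDOQI range already given in 3.4.1 d. Report them by arm and in the same windows (baseline, months 1-2, 4-6 and 10-12), as description beside the planned change in PTH level. Add a note that the desirable nocturnal level in 3.4.1 d may lie below 150 pg/mL, so a nocturnal patient below range is not necessarily off target.

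The range serves only to define reporting categories. No clinical target changes.

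The cost is a sentence of wording and the note. The PTH values are already scheduled in Table 9 C, so no visit, sample or test is added.
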